I undertake that I have submitted all documents completely.

Title of the Study : Evaluation of trigeminocardiac reflex development during extraction of mandibular impacted wisdom teeth

Responsible Researcher: Asst. [name]

Signature and Date :

KÜTAHYA HEALTH SCIENCES UNIVERSITY RECTORATE INTERVENTIONAL CLINICAL RESEARCH ETHICS COMMITTEE CLINICAL RESEARCH APPLICATION FORM

A. SUMMARY OF RESEARCH

Supportive	DDS, Asst. Professor , [name] [contact] [name]
Legal representative	DDS, Asst. Professor , [name]
Title of the research	Evaluation of trigeminocardiac reflex development during extraction of mandibular impacted wisdom teeth
Protocol code	-
Status of research	National 
- For academic purposes (Individual research project)
Nature of the research	
- Method clinical trial
Phase of	
- It is not a phase study.
Investigated medical condition or disease	Investigation of the frequency of trigeminocardiac reflex development during extraction of mandibular impacted wisdom teeth
Research methodology	In mandibular impacted wisdom tooth extractions, patients will be monitored (heart rate, blood pressure, oxygen saturation) and trigeminocardiac reflex development will be followed.
Place of production	Research product will not be used .
Comparison product / method	Research product will not be used
Place of production	Research product will not be used
Placebo	Research product will not be used
Place of production	Research product will not be used
Research arms(Arms-Interventions)	The study will include impacted wisdom teeth in the mandible. There will be 2 separate groups with the 2 most commonly used anaesthetic techniques (gow-gates (GG)/inferior alveolar nerve block (IAS)). The

	
tooth roots will be categorised as those that are between 1 mm and more than 1 mm closer to the nervus alveolaris inferior (Y-1) or more than 1 mm further away (Y-2). The research arms were planned as GG/Y-1, GG/Y-2, IAS/Y-1 and IAS/Y-2.


Purpose of the research
	
Trigeminocardiac reflex (TCR) was introduced to the scientific literature as an oculocardiac reflex with strabismus surgeries (1). In cases in which the V1 branch of the trigeminal nerve formed the afferent pathway, a clinical phenomenon in which vagal stimulation findings were observed was encountered. Since its publication in ophthalmological surgery in 1908, it has become a clinical picture well known to ophthalmologists and anaesthesiologists (2). The mastery and experience of the anaesthetist is of great importance in this picture which is met by manipulation of the ocular muscles. Recognition that the picture is a brainstem reflex involving the vagal pathway is critical in mastering the clinical situation. In the literature, it has been reported that V2 and V3 branches of the trigeminal nerve can also produce the reflex picture and the reflex can also be observed under local anaesthesia (3,4). The reflex is diagnosed with haemodynamic data (blood pressure, heart rate) which can be monitored non-invasively under local anaesthesia as well as under general anaesthesia.
 
TCHR is a physiological, life-threatening response characterised by sudden onset of severe bradycardia, hypotension and asystole, in which parasympathetic activation of the heart is observed with stimulation of the vagal nerve as a result of stimulation of any of the three branches of the trigeminal nerve (1). It is defined as a decrease in heart rate and mean arterial blood pressure by more than 20% compared to baseline or a heart rate of less than 60 beats per minute due to intraoperative traction or manipulation of the trigeminal nerve. The patients are normotensive or hypotensive (5). The afferent branch of the TCR arc is formed by the sensory nerve endings of the fifth cranial nerve and neuronal signals are sent to the trigeminal sensory nucleus via the Gasserian ganglion. The sensory nucleus of the afferent reflex branch of the trigeminal nerve is connected to the efferent pathway via short internuncial fibres in the reticular formation with the more distant motor nucleus of the vagus nerve. Cardioinhibitory efferent fibres originate from the motor nucleus of the vagus nerve and transmit vagus-mediated negative chronotropic and inotropic responses to the heart, terminating in the myocardium.
 
In the maxillofacial surgery literature, there are case reports reporting the development of trigeminocardiac reflex in orthognathic surgery, dental implant surgery and maxillofacial trauma surgery and prevalence studies for major surgeries (6,7,8). Haemodynamic changes and neurological-based emergencies (e.g. vasovagal syncope) are quite


	
common in routine oral surgical procedures performed under local anaesthesia (9).
 
In addition, in a study, a significant decrease in heart rate and blood pressure occurred during extraction of posterior mandibular teeth and it was pointed out that this may be related to the trigeminocardiac reflex (10). Extraction of impacted wisdom teeth is one of the commonly performed procedures in the field of oral and maxillofacial surgery. To the best of our knowledge, there is no study in the literature evaluating the development of TCR during mandibular impacted wisdom tooth extraction.
 
Our aim was to investigate the trigeminocardiac reflex during oral surgical procedures routinely performed under local anaesthesia. Our reasons for choosing mandibular impacted wisdom tooth surgery among oral surgeries for this purpose are; the proximity of the inferior alveolar nerve, which is the largest terminal branch of the V3 branch of the trigeminal nerve, to the tooth roots and the frequent observation of traction on the nerve, the fact that there may be differences in the depth of effect between anaesthetic techniques due to the variation of the mandibular nerve, and our clinical experience. There is no study in the literature evaluating the development of trigeminocardiac reflex during surgical treatment of mandibular wisdom teeth.

Scope of the research	
The study will be conducted on patients referred to KSBÜ Faculty of Dentistry, Department of Oral, Dental and Maxillofacial Surgery from Oral, Dental and Maxillofacial Radiology, who have an indication for extraction of impacted mandibular wisdom teeth under local anesthesia, who will undergo extraction of impacted wisdom teeth for the first time, who agree to have the surgical extraction of these teeth performed at KSBÜ Faculty of Dentistry, Department of Oral, Dental and Maxillofacial Surgery and who agree to participate in the study.
 
If there is a clinical necessity, cone beam computed tomography will be taken to evaluate the relationship of impacted wisdom teeth with the nervus alveolaris inferior and to evaluate their localization in the mandible in three dimensions. In patients who do not need tomography, the evaluation will be performed with Orthopantomogram film. The distance of the relevant wisdom tooth roots from the inferior alveolar nerve will be recorded.
 
During the procedure, Gow-Gates and nervus alveolaris inferior anesthesia techniques, which are the two most commonly used local anesthesia techniques in oral, dental and maxillofacial surgery practice, will be applied for the extraction of mandibular impacted teeth.
 
Patients will be divided into 2 groups according to the proximity of the wisdom tooth roots to the inferior alveolar nerve (1 mm and closer to the nerve / more than 1 mm away from the nerve) and 2 groups according to the anesthesia technique to be applied (Gow-Gates Block - Inferior alveolar block). Total research arm is 4.

In the research arms we have established, the follow-up of TKR that may occur during the procedure will be provided by monitoring the patients (Contec Medical Systems, Hebei, China.) Heart rate, systolic and diastolic blood pressure, oxygen saturation will be recorded during the procedure. The records will be taken in 4 stages: before starting the surgical procedure, during the application of local anesthesia, during the incision, during the elevation of the crown and root. Sudden changes that occur during the procedure will be recorded together with the process in which they occur.

(e.g. during local anesthesia)

Initial heart rate: 80 beats/min

End of procedure heart rate: 78 beats/min

Sudden presence of bradycardia or tachycardia during the procedure;

Sudden change in heart rate: 80>58 or 80>98)

During extraction of impacted wisdom teeth, a 20% decrease in heart rate and a decrease in heart rate below 60 will be considered as the development of TCR in parallel with the literature. The prevalence of TKR will be evaluated in 4 separate groups according to whether Gow-Gates anesthesia or nervus alveolaris inferior anesthesia is applied and whether the wisdom teeth are closer than 1 mm and 1 mm or further than 1 mm from the nervus alveolaris inferior.

During mandibular impacted wisdom tooth extraction, patients will be monitored and the following parameters will be evaluated:

1. Systolic blood pressure
2. Diastolic blood pressure
3. Oxygen saturation
4. Heart rate

The anxiety level of the patients will be assessed with the Amsterdam Preoperative Anxiety and Information Score Scale (APAIS) and State-Trait Anxiety Inventory (STAI-S) in order to differentiate TKR from common neurological emergencies (e.g. vasovagal syncope) due to dental phobia. State Anxiety Scale was developed in 1970 and its Turkish form was adapted in 1983 and validity and reliability study was conducted. APAIS was translated into Turkish for the first time in our country in 2007 and it was found that APAIS and STAI-S were correlated with each other in the studies conducted(11).

References

2. Aschner, B. (1908). Ueber einen Bisher noch nicht Beschriebenen Reflex vom Auge auf Kreislauf und Atmung: Verschwinden des Radialispulses bei Druck auf das. *Review of Oculocardiac Reflex When Facial Surgery*.

Evaluation of results (Outcome/Endpoint)	
During extraction of impacted wisdom teeth, a 20% decrease in heart rate and a decrease in heart rate below 60 will be considered as the development of TCR in parallel with the literature. The prevalence of TKR will be evaluated in 4 separate groups according to whether Gow-Gates anaesthesia or nervus alveolaris inferior anaesthesia is applied and whether the wisdom teeth are closer than 1 mm and 1 mm or further than 1 mm from the nervus alveolaris inferior.
 
During mandibular impacted wisdom tooth extraction, patients will be monitorised and the following parameters will be evaluated:
 
 1. Systolic blood pressure 2. Diastolic blood pressure 3. Oxygen saturation 4. Heart rate 
Patients will be asked to fill out the Situational Anxiety Inventory (STAI-S) and the Amsterdam Preoperative Anxiety and Information Scale (APAIS) forms before the procedure in order to evaluate the relationship between the haemodynamic changes that may occur and anxiety..

Statistical Analysis	
Since the study population was not known, the power and sample level of the study were calculated with reference to the study of Bohluli (2011). Bohluli (2011) studied with n=20 patients in his study. According to the study of Bohluli (2011), it is seen that n=20 patients planned to be included in the study planned the study with 90% power (in studies, values of 0.70 and above are considered valid and 0.80 is considered to be quite sufficient). In the study, it was determined that the effect size level was 0.42. The study is planned to be conducted on a total of 40 patients. The groups were determined equally as Group 1 (IAS / less than 1 mm distance) n=10, Group 2 (IAS / more than 1 mm distance) n=10, Group 3 (IAS / less than 1 mm distance) n=10 and Group 4 (IAS / more than 1 mm distance) n=10.
 
Regarding the analysis of the data; descriptive statistics will be presented with mean-d.deviation, median-IQR, frequency and percentage values. In order to examine whether the measurements in the study are different according to the characteristics of the study groups, independent Mann Wihtney U test and Kruskall Wallis test analyses are considered. Paired Wilcoxon test and Friedman test analysis can be applied in the evaluations of repeated measurements. In determining the times that are significant as a result of Friedman test, it is considered to be determined by All-pairwise method. Spearman correlation analysis will be applied to examine the relationships between the measurement values of the groups. Chi-square analysis will be performed for the proportional evaluations of the groups. In the study, p values less than 0.05 are considered significant. The analyses will be analysed with

	SPSS 25.0. Power level and effect size calculations calculated in the study were determined with G*Power Version 3.1.7.	
Coordinator	Coordinating centre	Kütahya Health Sciences University Faculty of Dentistry Department of Oral, Dental and Maxillofacial Surgery Kütahya Health Sciences University Faculty of Dentistry Department of Oral, Dental and Maxillofacial Surgery
	Coordinator (principal investigator in single-centre studies)	[name]
	Contact	[name] [contact]
Administrative Responsible (if applicable)	Name and surname	-
	Place of assignment	-
	Contact	-

Research centres

	Research centres	Principal Investigator (Area of Expertise) (Telephone)
1	Kütahya Health Sciences University Faculty of Dentistry Oral, Dental and Maxillofacial Surgery	[name] [name]

Information for bioavailability/bioequivalence studies

Licence status	Not a bioavailability/bioequivalence study.
Analytical centre/department	Not a bioavailability/bioequivalence study.
Tested research product	Not a bioavailability/bioequivalence study.
Reference product	Not a bioavailability/bioequivalence study.
Study design	Not a bioavailability/bioequivalence study.
Working periods	Not a bioavailability/bioequivalence study.
Previous studies	Not a bioavailability/bioequivalence study.

Properties of active substance

Resolution	No active substance will be used.
Bioavailability	No active substance will be used.
AUC	No active substance will be used.
C_{max}	No active substance will be used.
t_{max}	No active substance will be used.
Elimination Half Life (t_{1/2})	No active substance will be used.
Volume of Dispersion	No active substance will be used.
Binding to Proteins	No active substance will be used.
Food Effect	No active substance will be used.
Metabolism and Metabolites	No active substance will be used.
Breakthrough	No active substance will be used.
Accumulation	No active substance will be used.
Blood collection times	No active substance will be used.
Substance covered by biosafety	No active substance will be used.
Intra-individual variability constant of the active substance (%CV)	No active substance will be used.
Substance to be analysed	No active substance will be used.

B. OTHER INFORMATION

Risk / Benefit evaluation

There were no risk factors related to the study.

In this study, the development of trigeminocardiac reflex, which is an important issue during the extraction of impacted wisdom teeth and can be life-threatening in some cases, will be evaluated and important information about the frequency of trigeminocardiac reflex will be obtained.

Sensitive population/Vulnerable Group (*Vulnerable subjects*)

No sensitive population/vulnerable groups.

Payment to volunteers

Volunteers will not receive any payment.

Volunteer services

Volunteers will not receive any payment..

Research / volunteer documents (*additional documentation and recruitment procedure*)

In the study, patient cards will be created to note the age, gender, distance of the mandibular impacted wisdom teeth to the nervus alveolaris, systolic-diastolic blood pressure, heart rate, oxygen saturation and changes in these during the procedure.

At the same time, STAI-S (Situational Anxiety Test) and APAIS (Amsterdam Preoperative Anxiety and Information Form) will be used in adult patients to evaluate stress-anxiety and trigeminocardiac reflex development. The study will be conducted by including patients referred to KSBU Faculty of Dentistry, Department of Oral, Dental and Maxillofacial Surgery from Oral, Dental and Maxillofacial Radiology.

Independent data monitoring committee

There is no independent data monitoring committee in the study.

Sub-study

There is no sub-study in the research.

Biological material management

Biological material will not be transferred.

Facility / laboratory

No central technical facilities or laboratories will be used in the study

Delegation of tasks

There are no delegated duties.

Referral to other health authorities

There is no other country where research has been approved

Research-specific information

[figure not shown]
The trigeminocardiac reflex has been overshadowed by other vasovagal reflexes and is a well-defined clinical picture in ophthalmology. We believe that it should attract more attention in oral surgery where procedures are usually performed under local anaesthesia.

The study includes the addition of monitoring of patients to the treatment processes routinely performed in our clinic.

C. RESEARCH TEAM LIST

Centre Name	Kütahya Health Sciences University Faculty of Dentistry Oral, Dental and Maxillofacial Surgery			
Address	[name]			
Mission	Name Surname	Title	Education	İKU Training (present/absent))
Principal Investigator	[name]	Asst. [name] and Maxillofacial Surgery	None
Assistant Researcher	[name]	Resarch Asst	Oral and Maxillofacial Surgery	None
Assistant Researcher	[name]	Resarch Asst	Oral and Maxillofacial Surgery	None
Counsellor	[name]	Asst. [name] and Reanimation	None
Counsellor	[name]	[name] and Maxillofacial Surgery	None

D. RESEARCH DESIGN DIAGRAM

E. ASSESSMENT CHART (Schedule of Assessments)

Evaluation	Tarama	Operasyon
Informed Voluntary Consent Form		X
Demographic information	X	
Medical history/ General physical examination	X	
Clinical data		X
CBCT	X	
Inclusion/exclusion criteria	X	
Intra-op data		X

F. ETHICS COMMITTEE INFORMATION

	There is a previous rejection decision by the ethics committee of the research	
	Name of the ethics committee	Kütahya Health Sciences University Non-Interventional Clinical Research Ethics Committee
	Date of decision	
	Decision no.	

This section must be filled in when applying to the Turkish Medicines and Medical Devices Agency.
		
	Ethics committee application was made for approval of the research	
	Name of the ethics committee	-
	Application date	-
	There is ethics committee approval for the research..	
	Name of the ethics committee	-
	Date of decision	-
	Decision no.	-

G. RELATED DOCUMENTS

1. Research protocol
2. Protocol signature page (signed by the coordinator in multicentre studies and the principal investigator in single-centre studies) Bilgilendirilmiş gönüllü olur formu (BGOF)
3. Research brochure
4. Case report form
5. Insurance documents
6. (insurance certificate, insurance policy, insurance endorsements, general and special conditions of the policy)
7. Research budget form
8. CVs
9. (of the principal investigators)
10. Authorisation documents (if valid)
11. (with Turkish translations certified by a notary public or sworn translator)
12. Research team documents (if applicable)
13. (all documents used only by the research team or used to inform the research team, such as application instructions, information texts, doctors' letters, etc.)
14. Volunteer documents (if applicable)

- 15.** (patient card, patient diary, questionnaire, instructions for use, application instructions, information texts, posters, brochures, information documents explaining the intended use of the materials to be given to volunteers (electronic diary, cooler bag, etc.))
- 16.** Ethics committee decision (original and certified copy of the original)
- 17.** Research product file (if required)
- 18.** GMP Certificate/Document (apostilled) (if applicable)
- 19.** If the research is for academic purposes, a wet signed document approved by an authorised person other than the applicant stating that the research is for academic purposes
Only for bioavailability/bioequivalence studies;
- 20.** Certificate of supply of the investigational product and reference product(s) (invoice/package photocopy with serial number and expiry date)
- 21.** Certificate of analysis of the research product

H. DOCUMENTS TO BE PHYSICALLY SUBMITTED

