PHASE AND TYPE OF RESEARCH	Phase 1	
	Phase 2	
	Phase 3	
	Phase 4	
	Observational drug study	
	Medical device clinical research	

	Performance evaluation studies conducted with in vitro medical diagnostic devices	
	Non-drug clinical research	
Please specify if other:		

Research hypothesis:

$\mu \neq 0$ hypothesis: During extraction of mandibular impacted wisdom teeth, the trigeminocardiac reflex does not occur with stimulation of the peripheral branches of the trigeminal nerve.

$\mu = 0$ hypothesis: During extraction of mandibular impacted wisdom teeth, a trigeminocardiac reflex occurs by stimulation of the peripheral branches of the trigeminal nerve.

Introduction-Purpose Section

The trigeminocardiac reflex (TCR) has entered the scientific literature as an oculocardiac reflex with strabismus surgeries (1). In cases where the V1 branch of the trigeminal nerve forms the afferent pathway of the V1 branch of the trigeminal nerve, a clinical phenomenon with vagal stimulation findings has been encountered. Since the publication of TCR in ophthalmological surgery in 1908, it has become a well-known clinical picture for ophthalmologists and anesthetists (2). The anesthetist's mastery and experience in this picture, which is met by manipulation of the ocular muscles, is of great importance. Recognition that the picture is a brainstem reflex involving the vagal pathway is critical in mastering the clinical situation. In the literature, it has been reported that V2 and V3 branches of the trigeminal nerve can also produce the reflex picture and the reflex can be seen under local anesthesia. (3,4). Reflex is diagnosed under local anesthesia as well as under general anesthesia with hemodynamic data (blood pressure, heart rate) that can be monitored non-invasively.

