TCR is a physiological, life-threatening response with sudden onset of severe bradycardia, hypotension and asystole with parasympathetic activation of the heart due to stimulation of the vagal nerve as a result of stimulation of any of the three branches of the trigeminal nerve. (1). It is defined as a decrease in heart rate and mean arterial blood pressure by more than 20% from baseline or a heart rate of less than 60 beats per minute due to intraoperative traction or manipulation of the trigeminal nerve. The afferent branch of the trigeminocardiac reflex arc is formed by the sensory nerve endings of the fifth cranial nerve. Neuronal signals are sent to the trigeminal sensory nucleus via the Gasserian ganglion. The sensory nucleus of the afferent reflex branch of the trigeminal nerve connects to the efferent pathway via short internuncial fibres in the reticular formation with the more distant motor nucleus of the vagus nerve. Cardioinhibitory efferent fibres originate from the motor nucleus of the vagus nerve. It transmits vagus-mediated negative chronotropic and inotropic responses to the heart and terminates in the myocardium (5).

In the maxillofacial surgery literature, there are case reports reporting the development of trigeminocardiac reflex in orthognathic surgery, dental implant surgery and maxillofacial trauma surgery and prevalence studies for major surgeries (6,7,8). Haemodynamic changes and neurological-based emergencies (e.g. vasovagal syncope) are quite common in routine oral surgical procedures performed under local anaesthesia (9).

In addition, in a study, it was noted that a significant decrease in heart rate and blood pressure occurred during extraction of posterior mandibular teeth and this may be related to the trigeminocardiac reflex (10). Extraction of impacted wisdom teeth is one of the commonly performed procedures in the field of oral and maxillofacial surgery. To the best of our knowledge, there is no study in the literature evaluating the development of TCR during mandibular impacted wisdom tooth extraction.

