In the research arms we have established, the follow-up of TCR that may occur during the procedure will be provided by monitoring the patients (Contec Medical Systems, Hebei, China.) Heart rate, systolic and diastolic blood pressure, oxygen saturation will be recorded during the procedure. The records will be taken in 4 stages: before starting the surgical procedure, during the application of local anaesthesia, during the incision, during the elevation of the crown and root. Sudden changes that occur during the procedure will be recorded together with the process in which they occur.

(e.g. during local anesthesia)

Initial heart rate: 80 beats/min

End of procedure heart rate: 78 beats/min

Sudden presence of bradycardia or tachycardia during the procedure;

Sudden change in heart rate: 80>58 or 80>98)

During extraction of impacted wisdom teeth, a 20% decrease in heart rate and a decrease in heart rate below 60 will be considered as the development of TCR in parallel with the literature. The prevalence of TKR will be evaluated in 4 separate groups according to whether Gow-Gates anaesthesia or nervus alveolaris inferior anaesthesia is applied and whether the wisdom teeth are closer than 1 mm and 1 mm or further than 1 mm from the nervus alveolaris inferior.

During mandibular impacted wisdom tooth extraction, patients will be monitored and the following parameters will be evaluated:

1. Systolic blood pressure
2. Diastolic blood pressure
3. Oxygen saturation
4. Heart rate

The anxiety level of the patients will be assessed with the Amsterdam Preoperative Anxiety and Information Score Scale (APAIS) and State-Trait Anxiety Inventory (STAI-S) in order to differentiate TKR from common neurological emergencies (e.g. vasovagal syncope) due to dental phobia. State Anxiety Scale was developed in 1970 and its Turkish form was adapted in 1983 and validity and reliability study was conducted. APAIS was translated into Turkish for the first time in our country in 2007 and it was found that APAIS and STAI-S were correlated with each other in the studies conducted(11).

STAI-S (The State-Trait Anxiety Inventory)

Amsterdam Preoperative Anxiety and Information Scale (APAIS)

	Not all 1	2	3	4	Very much 5
I am worried about anesthetics					
The anesthetics is on my mind continually					
. I would like to know as much as possible about the anesthetic					
I am worried about the procedure.					
The procedure is on my mind continually.					

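### The rule that classifies TCR does not match the only TCR definition with thresholds in the protocol, and the difference is not explained

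*Protocol*

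**What the plan says.** **Definition.** The Introduction-Purpose Section of the Protocol sets these thresholds for TCR: "a decrease in heart rate and mean arterial blood pressure by more than 20% from baseline or a heart rate of less than 60 beats". The same sentence then ties the event to a cause: "due to intraoperative traction or manipulation of the trigeminal nerve". The application form repeats the definition under *Purpose of the research*: "a decrease in heart rate and mean arterial blood pressure by more than 20% compared to baseline or a heart rate of less than 60". No other text in the document puts thresholds on TCR as a condition. The introduction also says: "Reflex is diagnosed under local anesthesia as well as under general anesthesia with hemodynamic data (blood pressure, heart rate").

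**Outcome rule.** The Materials and Methods Section, *Scope of the research* and *Evaluation of results (Outcome/Endpoint)* share one sentence about events during extraction: "a 20% decrease in heart rate and a decrease in heart rate below 60 will be considered as the development of TCR". It adds that this is in line with the literature.

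**Recording.** Heart rate, systolic and diastolic pressure and oxygen saturation are recorded: "The records will be taken in 4 stages: before starting the surgical procedure", then at local anaesthesia, at incision, and at elevation of crown and root. Sudden changes are noted with the step at which they occur. The one worked example of a fall is a heart rate going from 80 to 58. The anxiety scales are collected "in order to differentiate TKR from common neurological emergencies (e.g. vasovagal syncope) due to dental phobia".

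**The concern.** Four things differ between definition and rule.

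- 'Or' becomes 'and'.
- The MAP limb is gone.
- 'More than 20%' becomes '20%'.
- A causal condition becomes a statement of timing.

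None of these changes is mentioned or justified.

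The study sets out to report how often TCR occurs (*Investigated medical condition or disease*; *Risk / Benefit evaluation*) and to compare that frequency across four groups of 10. The case definition therefore determines the main result. A reader who takes the definition from the introduction and the prevalence from the results would not know that the two refer to different events.

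**Working it through.** The protocol gives no figure to reproduce here. The check applies both criteria to the same heart rates.

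**Inputs.** Let b be the baseline rate and n the lowest rate, in whole beats, with b at least 60. The criteria are those quoted above. In the definition, the two 20% falls are read as both required.

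- Definition, haemodynamic part: n < 60, or (n < 0.8b and MAP falls by more than 20%).
- Rule, strict 'and': n < 60 and n ≤ 0.8b.
- Rule, 'and' meaning either: n < 60 or n ≤ 0.8b.

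**The protocol's own example.** 80 to 58 is (80 − 58)/80 = 27.5%, and 58 is below 60. It meets the definition and both readings of the rule, so it does not settle the difference.

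**Strict 'and'.** Every case under the rule has n < 60, so it also meets the definition. The reverse fails. The two heart-rate limits meet at 0.8 × 75 = 60.

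| Baseline | 0.8b | Lowest rates meeting the definition but not the rule | MAP fall above 20% needed? |
|---|---|---|---|
| 65 | 52 | 53–59 | no |
| 70 | 56 | 57–59 | no |
| 80 | 64 | 60–63 | yes |
| 90 | 72 | 60–71 | yes |
| 100 | 80 | 60–79 | yes |

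Examples: 70 to 58 is 12/70 = 17.1%; 90 to 70 is 20/90 = 22.2%.

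Above a baseline of 75 the 20% figure no longer decides anything, because the rate must still drop below 60. The fall must then exceed (b − 60)/b: 20/80 = 25% at 80, 30/90 = 33.3% at 90, and 40/100 = 40% at 100.

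**'And' meaning either.** Now every haemodynamic case under the definition also meets the rule, and the reverse fails. 80 to 62 is 18/80 = 22.5%. Without a MAP fall above 20% it is TCR by the rule and not by the definition. The mismatch remains, with its direction reversed.

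**Cause.** The definition requires that traction or manipulation produced the fall. The rule requires only that the fall happened during extraction. The step is recorded and the anxiety scales are collected, but neither enters the rule as a condition. *Evaluation of results* states the purpose of the scales as relating haemodynamic change to anxiety.

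**Size per patient.** One reclassified patient is 1/10 = 10 percentage points in a group and 1/40 = 2.5 points overall.

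**The case against.** The rule has the same wording in all three places, one of them the outcome section, while the definition stands in background text. A study may adopt a narrower case definition than its introduction describes. That is fair, and on a strict reading an analyst could apply the rule. What stands is that the departure is neither acknowledged nor explained, and that 'and' can be read in two ways with opposite consequences.

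On blood pressure, the sentence after the definition in *Purpose of the research* says patients may have normal pressure, and the below-60 limb needs no pressure fall. So the protocol already allows TCR without hypotension. This softens the criticism but does not explain the dropped MAP limb, since the definition still uses MAP in its other limb.

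On cause, the wording about extraction, the recording of steps and the anxiety scales show that the authors had the problem in mind. It would be too strong to say that cause is ignored, or that vasovagal falls will be counted as TCR. The fair statement is that these elements are not made conditions of the rule.

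Three stronger conclusions might be inferred, and the document supports none of them.

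- *The rule undercounts TCR.* This holds only for strict 'and' and only on haemodynamics. The causal clause narrows the definition and can act the other way, so the net direction is unknown.
- *The appeal to the literature ("a decrease in heart rate below 60 will be considered as the development of TCR in parallel with the literature") is false.* It refers to published work that is not available here. Only the mismatch inside the protocol can be shown.
- *The choice of rule would change the significance of the group comparison.* That depends on event counts the protocol does not give.

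**Conclusion.** The point stands as an unexplained inconsistency in the definition of the study's main outcome, under either reading of 'and'. The discordant heart rates are ordinary ones on both sides of a baseline of 75. Each reclassified patient moves a group's prevalence by 10 points. The number of such patients cannot be derived, because the protocol gives no distribution of heart rate or pressure.

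The threshold figures assume baselines of 60 or more; the subset statements set cause aside. The planned analyses of continuous heart rate and pressure are not affected. Nothing here says which criterion is clinically right.

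**What to change.** Before any data are classified, reconcile the Introduction-Purpose Section, the Materials and Methods Section, *Purpose of the research*, *Scope of the research* and *Evaluation of results* into one rule with the same wording throughout. The rule should state:

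1. whether the heart-rate criteria are joined by 'and' or 'or';
2. whether MAP is part of it;
3. whether the threshold is 20% or more than 20%;
4. whether the causal condition applies.

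If the final rule departs from the definition in the introduction, give the reason. Report TCR prevalence in the four groups under the other stated definition as a sensitivity analysis, with MAP derived from the recorded systolic and diastolic pressures.

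The cost is wording, one derived variable and one extra table. The patient card described under *Research / volunteer documents* already holds the pressures, the heart rate and their changes during the procedure. The downside is two prevalence figures to report and explain.
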